5.7 Duration of Follow-up

For this protocol, all patients, including those who discontinue protocol therapy early, will be followed for response until progression, even if non-protocol therapy is initiated, and for survival for 5 years from the date of registration.

6. Measurement of Effect

6.1 Time to Progression

This interval will be measured from the date of entry on the study to the appearance of new metastatic lesions or objective tumor progression.

6.2 Methods of Measurement

Imaging based evaluation is preferred to evaluation by clinical examination. The same imaging modality must be used throughout the disease evaluation.

CT and MRI: CT and magnetic resonance imaging (MRI) are the best currently available and most reproducible methods for measuring target lesions.

Chest X-Ray: Lesions on chest x-ray are acceptable as measurable lesions when they are clearly defined and surrounded by an aerated lung. However, CT is preferable.

Tumor Markers: Tumor markers alone cannot be used to assess response.

Clinical Examination: Clinically detected lesions will only be considered measurable when they are superficial (e.g., skin nodules and palpable lymph nodes). For skin lesions, documentation by color photography, including a ruler to estimate size of the lesion, is recommended. Photographs should be retained at the institution.

Cytology and Histology: Cytologic confirmation of the neoplastic nature of any effusion that appears or worsens during treatment is required when the measurable tumor has met response or stable disease criteria.

Ultrasound: Ultrasound may be used only as an alternative to clinical measurements for superficial palpable lymph nodes, subcutaneous lesions, and thyroid nodules.

7. Schedule of Assessments

NOTE: There is a window of ± 1 week available for scheduling treatment and/or procedures at the discretion of the Investigator/Sub-investigator. This applies also if a course is missed or a subject's treatment and/or testing day(s) need to be rescheduled due to the subject's inability to comply with the study calendar (i.e., hospitalizations, business, vacation plans, travel from long distances for study treatment, in advance of the scheduled date to allow ready access to the result(s), reduce financial burden on the subject [i.e. non-UPMC insurance coverage] or reduce travel inconvenience, illness, transportation issues, holidays, family emergencies, etc.).

	Screening ¹	Day -5 ± -2	Adjuvant Nivolumab	EOT ¹⁰	LTFU
Medical history, physical exam, vital signs	X	X	X	X	
Height	X				
Weight	X	X	X	X	
ECOG performance status	X	X	X	X	
CBC w/diff, platelets	X ¹	X	X	X	
Amylase, lipase	X		X		
TSH	X ⁷		X		
Serum chemistry	X ¹	X	X	X	
Serum pregnancy test	X ¹				
QOL questionnaires	X			X	X ⁹
Adverse event evaluation	X	X	X	X	
Disease evaluation by clinical methods ²	X		X ²	X ²	X ²
CT scan/MRI ¹²	X		X ²	X ²	X ²
SLP consult with MBS ³	X			X	X ³
Tumor tissue	X				
Blood and saliva biomarkers ⁸		X	X	X	X
IMRT					
Nivolumab ^{5,6}		X	X		

¹Pre-study laboratory assessments should be done ≤ 4 weeks before registration.

²Disease evaluation by clinical methods and a CT and/or MRI to assess all measurable or non-measurable sites of disease will be obtained at screening (≤ 4 weeks before registration), symptomatically during IMRT, every 3 months during adjuvant nivolumab treatment starting from end of radiation therapy, every 6 months for 3 years, and annually for 2 more years to confirm standard of care assessments.

³SLP = speech language pathologist; MBS = modified barium swallow; Required for participation at screening and 6 and 24 months after treatment, and if MBS is performed as standard of care.

⁴All labs may be completed within 7 days of surgery.

⁵Nivolumab 240mg IV every two weeks

⁶Nivolumab 480mg every 4 weeks for 6 doses.

⁷TSH to be drawn for baseline status. Is not an eligibility criterion

⁸Blood biomarkers will be drawn at screening, week 0: Day -3 (± 2 Days), every 4 Weeks (post Week 4) x 24 Weeks (± 7 Days), EOT. For LTFU: Every 3 Months x 24 Months then every 6 Months x 3-5 Years from completion of radiation therapy

- a. Serum Cytokines/Chemokines
- b. HPV DNA (blood & saliva)
- c. Tumor antigen specific cellular immunity
- d. Lymphocyte Markers

⁹QOL's will be collected for LTFU at 3, 6, 12, 24 months from completion of radiation therapy

¹⁰ EOT should coincide with 6 month CT scan post radiation therapy.

8. Nivolumab Formulation and Procurement

Product Description / Class and Dosage Form	Potency	IP/Non-IMP	Blinding	Packaging	Storage Conditions (per label)
BMS-936558-01 (Nivolumab) Solution for Injection*	100 mg (10 mg/mL)	IP	Open Label	10 mL per vial (5 or 10 vials/carton)	Store at 2° - 8 °C. Protect from light and freezing.

*May be labeled as either "BMS-936558-01" or "Nivolumab"

Investigational Product

An investigational product, also known as investigational medicinal product in some regions, is defined as a pharmaceutical form of an active substance or placebo being tested or used as a reference in a clinical study, including products already with a marketing authorization but used or assembled (formulated or packaged) in a way different from the authorized form, or used for an unauthorized indication, or when used to gain further information about the authorized form. The investigational product should be stored in a secure area according to local regulations. It is the responsibility of the investigator to ensure that investigational product is only dispensed to study subjects. The investigational product must be dispensed only from official study sites by authorized personnel according to local regulations. In this protocol, the investigational product is nivolumab.

Storage and Dispensing

The product storage manager should ensure that the study drug is stored in accordance with the environmental conditions (temperature, light, and humidity) as determined by BMS. If concerns regarding the quality or appearance of the study drug arise, the study drug should not be dispensed and contact BMS immediately.

Investigational product documentation (whether supplied by BMS or not) must be maintained that includes all processes required to ensure drug is accurately administered. This includes documentation of drug storage, administration and, as applicable, storage temperatures, reconstitution, and use of required processes (eg, required diluents, administration sets).

Infusion-related supplies (eg, IV bags, in-line filters, 0.9% sodium chloride injection, 5% dextrose injection) will not be supplied by the sponsor and should be purchased locally if permitted by local regulations.

Please refer to the current version of the Investigator Brochure and/or pharmacy reference sheets for complete storage, handling, dispensing, and infusion information for nivolumab.

Nivolumab is to be administered as an IV infusion. At the end of the infusion, flush the line with a sufficient quantity of dextrose or normal saline.

Selection and Timing of Dose for Each Subject

Dosing modifications:

There will be no dose modifications allowed for the management of toxicities of individual subjects.

Dosing window:

Subjects may be dosed no less than 12 days between doses. A dose given more than 3 days after the intended dose date will be considered a delay. A maximum delay of 6 weeks between doses is allowed.

Treatment Compliance

Treatment compliance will be monitored by drug accountability as well as the subject's medical record and eCRF.

Destruction of Study Drug

For this study, study drugs (those supplied by BMS or sourced by the investigator) such as partially used study drug containers, vials and syringes must be destroyed on site.

Any unused study drugs can only be destroyed after being inspected and reconciled by the responsible Study Monitor unless study drug containers must be immediately destroyed as required for safety, or to meet local regulations (eg, cytotoxic agents or biologics).

On-site destruction is allowed provided the following minimal standards are met:

- On-site disposal practices must not expose humans to risks from the drug.
- On-site disposal practices and procedures are in agreement with applicable laws and regulations, including any special requirements for controlled or hazardous substances.
- Written procedures for on-site disposal are available and followed. The procedures must be filed with the site's standard operating procedures (SOPs) and a copy provided to BMS upon request.
- Records are maintained that allow for traceability of each container, including the date disposed of, quantity disposed, and identification of the person disposing the containers. The method of disposal, i.e., incinerator, licensed sanitary landfill, or licensed waste disposal vendor must be documented.
- Accountability and disposal records are complete, up-to-date, and available for the Monitor to review throughout the clinical trial period.

If conditions for destruction cannot be met the responsible Study Monitor will make arrangements for return of study drug.

It is the investigator's responsibility to arrange for disposal of all empty containers, provided that procedures for proper disposal have been established according to applicable federal, state, local, and institutional guidelines and procedures, and provided that appropriate records of disposal are kept.

9. Statistical Considerations

The purpose of this phase II trial of p16⁺ OPSCC patients that will undergo transoral surgery followed by de-intensified adjuvant radiotherapy plus nivolumab is to demonstrate equivalent oncologic outcome with fewer adverse effects and improved quality of life when compared to the standard of care

9.1 Objectives

The dual primary objectives of this phase II study are (1) test the hypothesis that the proposed adjuvant de-escalation strategy (TORS + 50Gy RT + Nivolumab cancer) has equivalent (non-inferior) 2-year PFS. PFS is survival without local, regional or distant disease progression; patients who do not progress or die while disease – free will be censored and (2) to demonstrate a reduction in the rate of PEG tube dependence at one year.

Secondary objectives include estimating recurrence patterns, assessing quality of life (QOL) and swallowing function before and after treatment and evaluating toxicity.

With improved outcomes for p16+ oropharyngeal cancers treatment de-escalation is a critical and topical subject for a controlled clinical. This trial tests the hypothesis that de-escalating treatment of intermediate risk p16+ oropharyngeal cancer patients benefits them by providing equivalent oncologic outcome with superior quality of life.

The first hypothesis to be tested is that oncologic outcome following de-escalation is clinically equivalent to conventional standard systemic therapy with transoral robotic surgery (TORS) plus adjuvant cisplatin and 60-66 Gy radiation. The definition of non-inferiority is clearly within a desired clinical window of equivalence, defined as 2-year PFS, not less than 10% lower than expected under standard-of-care. Therefore, the design is to establish the non-inferiority of the experimental therapy (TORS + Nivolumab + 50 Gy radiation). The second hypothesis to be tested is de-escalation is warranted, by virtue of a clinically meaningful improvement in quality of life as measured by reduced G tube patency.

The decision to select a single arm trial is based on the following: A two arm randomized non-inferiority trial would be prohibitively expensive, infeasible (approximately 600 patients would be needed) and delay results for five years. This single-arm trial is feasible and is powered to produce a definitive result in 3 years from 1st accrual. The comparison is a to large-well characterized contemporaneous subset of the ECOG 3311 trial with similar pathologic features as we propose in our new trial, that received cisplatin and standard dose radiotherapy in Arm D of ECOG 3311. Patients recruited to ECOG 3311 are expected to be similar to our patients at the University of Pittsburgh, a large tertiary-care academic medical center, in part since we were the #1 largest accrue in the US to ECOG 3311 ([name] is PI of that trial as well).

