Given the favorable prognosis that has been well described for the HPV-associated OPSCC patient, we hypothesize that the prescribed RT dose may be safely reduced following transoral surgical resection and pathologic risk stratification for the risk of relapse. On the other hand, patients with traditional high-risk pathologic features would be treated with current CRT to 66 Gy. Similarly, low-risk patients could be observed. For the intermediate-risk patient, we hypothesize that the prescribed dose may be safely reduced from a standard intermediate-risk prescription of 60 Gy to 50 Gy without compromise in local-regional control rates. Moreover, we expect a reduction in the development of both objective and patient-reported measures of late RT toxicities.

Radiotherapy dose reduction has been studied in the recently completed E1308. This study prospectively examined the oncologic efficacy of reducing the RT dose to 54 Gy following a complete clinical response to induction CT. No pathologic evaluation of the primary site was required. The long-term results of this trial remain pending but early locoregional control (LRC) and disease-free survival (DFS) in complete responders, excluding T4 cancers and > 10 pk-yr tobacco exposure, are encouraging and comparable to standard dose radiation. Thus, the current hypothesis is predicated on transoral resection leaving a comparable, if not favorable, microscopic burden of residual cancer cells. Theoretical mathematical modeling of radiation response and cancer control in human solid tumors has been extensively reported and is based on the modeling

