While awaiting results of the completed RTOG 1016 de-escalation trial for HPV + OPC comparing Cisplatin to Cetuximab with standard radiation (70 Gy), the NRG is currently conducting a Phase II randomized trial of de-escalated radiation (60 Gy) +/- cisplatin chemotherapy for favorable risk OPC-SCC, HPV16+, < 10 pack-yrs smoking. ECOG 1308, a phase II randomized risk-adaptive trial reported LRC > 95% at 2 years, in which patients demonstrating a complete clinical response at the primary site after induction Chemo-Biologic therapy, received substantial de-escalated radiotherapy (54 G) + Cetuximab, with no compromise in LRC or DFS.

Surgical Risk Adaptive Strategies for HPV+OPC:

Recent enthusiasm has emerged for the utilization of trans-oral surgery with neck dissection for HPV 16+ OPC in which Stage I-II, favorable patients are observed rather than receive adjuvant therapy with few primary or regional neck failures. (T1-2, N0-1).⁴ However, risk stratification to define intermediate and high-risk groups in the post- surgical setting for HPV+ OPC is unclear. The ECOG is currently conducting a randomized, risk adjusted treatment Intensity Trial (ECOG 3311) in which HPV16+ OPC, stage III-IV (cT1-2, N1-2b) undergo TORS followed by either observation (FR), IMRT alone to 50 or 60 Gy (IR) or for higher risk patients, IMRT 66 Gy + weekly Cisplatin, with a primary endpoint of PFS at 2 years. However, the doses in this trial for traditional IR and HR are equivalent or even higher than the doses currently employed in the Phase II NRG trial for definitive cases. Smoking status is not part of the randomization or associated with risk groups but is a stratification variable. Prior to HPV discovery, RTOG 9501, and the EORTC, based on two similar trials with extended follow-up > 10 years, re-defined high risk as either having + margins/ and or +ENE with marginal benefit to addition of cisplatin. Patients were not stratified or randomized based on smoking history. HPV as a causative factor in OPC was not known at that time. Subsequently, N2 lymph nodes stage was changed to intermediate risk (with no benefit to Cisplatin), forming the basis for RTOG 0920, stratified by HPV status, a randomized trial for intermediate risk patients to receive 60 Gy + /-

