2.1 Primary Objective

The dual primary objectives of the study are (1) to test the hypothesis that the proposed adjuvant de-escalation strategy (TORS + 50Gy RT + Nivolumab cancer) is equivalent (non-inferior) to current standard of care cisplatin chemotherapy + standard 60-66 Gy radiation, and (2) to demonstrate a reduction in the rate of PEG tube dependence at one year.

Primary Hypotheses: We hypothesize that HPV + OPC is a distinct immunologic disease with a more favorable prognosis compared to HPV- OPC and represents a novel opportunity for de-escalation strategies in the adjuvant setting in Intermediate-Risk p16+ OPC groups after trans-oral resection (TORS). Risk-Adaptive de-escalation through a combination of TORS surgical resection followed by de-escalated RT (50 Gy accelerated fractionation) and concurrent Nivolumab immunotherapy in HPV+ OPC patients will result in similar PFS compared to historical results of standard CRT studies (60-66 Gy +/- Cisplatin) in the adjuvant setting, typically recommended for Intermediate and High Risk patients (HPV-, >4 metastatic nodes, + extensive ENE, + margins), as well as improvement in secondary endpoints of reduced toxicity, and patient QOL measures.

We further hypothesize that RT combined with concurrent and adjuvant Nivolumab will offer similar PFS outcomes to historical trials using cisplatin-based CRT through reduced tumor microenvironment immune suppression, enhanced systemic immune activation and response, and reduced toxicity by eliminating standard chemotherapy and allowing de-escalated RT.

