4.1 Required Information

Patient must be stratified/classified into one of the following risk categories:

- **Tobacco <10 pk-yr: T0-3 plus any one of the following: >N2b (> 5 LN's +), N2c/N3, +ENE >1 mm, or + margin (if approved by surgical chair) OR**
- **Tobacco >10 pk-yr: T0-3 plus any one of the following: any N2, N3, +ENE >1 mm, or + margin (if approved by surgical chair)**

Patients not categorized into the appropriate risk category will be considered ineligible for the study.

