9.2 Sample Size and Accrual Rate

Approximately 135 eligible subjects will be enrolled in this multicenter clinical trial that will be conducted at approximately 25 UPMC sites and up to 5 external sites in North America.

The first primary objective is to demonstrate that TORS with de-escalation RT (50Gy) and Nivolumab is equivalent (not inferior) to the standard of care of chemotherapy + standard 60-66 Gy radiation. The first primary endpoint is probability of progression free survival where an event is any type of disease progression or recurrence (local, regional or distant). In this definition deaths from other cancers, other non-cancer causes or treatment related deaths are censored. The historical control for the study is based part upon the results of Huang ⁹ in which the probability of 3 year OS was approximately 65% for high risk (Group III, T4 or N3, age < 70) HPV+ patients treated with chemoradiation and that 3 year OS is an approximation of two year PFS. Since there is not an ideal, published cohort to use, the trial is designed to investigate whether TORS with 50 Gy RT + Nivolumab is not inferior to standard of care chemotherapy + standard 60-66 Gy radiation.

We plan to devote 2 years of accrual and one year of additional follow-up. We assume that the experimental arm is not inferior to the standard if the 2-year PFS is not less than 55%, 10% less than the assumed standard. Thus 55% 2-year TTP for de-escalation RT + Nivolumab is considered not inferior to the 65% 2-year PFS for Cisplatin + 60-66 Gy RT.

Using a one-tailed exponential test (using the maximum likelihood estimator for the hazard rate of the exponential distribution) at $\alpha = .10$, 135 patients will provide 90% power to reject the null hypothesis that the experimental arm is inferior (less than 55% 2-year PFS) when the underlying 2-year PFS is 65%.

The second primary objective is to demonstrate reduction in feeding tube dependence. We will compare 1-year PEG tube dependence for patients who have not progressed to the SOC. Based on

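### The cisplatin + 60-66 Gy reference and the ECOG 3311 Arm D similarity statement do not cover everyone enrolled, so the pooled tests cannot by themselves carry a cisplatin-specific conclusion

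*Combined protocol and SAP*

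**What the plan says.** **Comparator.** Section 9.1 sets the PFS hypothesis against transoral surgery "plus adjuvant cisplatin and 60-66 Gy radiation". Its rationale for a single arm points to a subset of ECOG 3311 with "similar pathologic features as we propose in our new trial, that received cisplatin and standard dose radiotherapy in Arm D of ECOG 3311".

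**Who is enrolled.** Sections 3.1 and 4.1 admit "Tobacco >10 pk-yr: T0-3 plus any one of the following: any N2, N3", among other routes. For a smoker above 10 pack-years, N2 is enough, without ENE, a positive margin or a minimum node count. The summary before the biomarker rationale in section 1.5 says that the trial takes in both the intermediate- and the high-risk cohorts of ECOG 3311.

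**What ECOG 3311 gave.** Section 1.5 reports, after observation for favourable risk, "IMRT alone to 50 or 60 Gy (IR) or for higher risk patients, IMRT 66 Gy + weekly Cisplatin". When it introduces a different trial (RTOG 0920), it also says that "N2 lymph nodes stage was changed to intermediate risk (with no benefit to Cisplatin". Elsewhere it describes the intermediate-risk dose as being "reduced from a standard intermediate-risk prescription of 60 Gy to 50 Gy".

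**What is tested.** In section 9.2 the PFS null is 55%, which is 10 points below an assumed 65%. The 65% rests in part on 3-year OS in T4 or N3 HPV+ patients given chemoradiation. The PEG null is 15%, from unpublished RTOG 0234 results with RT, cisplatin and cetuximab (11 of 67). Each co-primary is one test on one pooled group: 135 patients for PFS, and about 108 progression-free patients for PEG.

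**The concern.** A cisplatin-based reference is informative for patients whose reference treatment contains cisplatin. By section 1.5, the intermediate-risk part of ECOG 3311 did not receive it, and this trial enrols that part too. The similarity statement in section 9.1 therefore fails for some of the people being analysed.

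The stakes differ by endpoint. Sections 1.3 and 1.4 say that concurrent chemotherapy adds to late swallowing injury. A 15% tube rate taken from a cisplatin-plus-cetuximab regimen is then likely to be too high a bar for patients without high-risk features, and including them makes a reduction easier to declare. For PFS, a pooled success could be worded as non-inferiority to cisplatin chemoradiation even if patients with high-risk features sat exactly at the unacceptable 55%, carried by others doing better.

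**Working it through.** The documents do not give the share *f* of patients without high-risk features, or their outcomes. I assume *f* = 20%, 30% and 50%, and the same share among the 108 as among the 135.

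**1. PEG: the plan's own figure.** Inputs (section 9.2): n = 108, one-sided alpha .06, 15% versus 7.5%. The rule is to reject if X ≤ c, with c the largest value for which P(X ≤ c | 108, .15) ≤ .06. This gives c = 10, with exact alpha .0559 (c = 11 gives .0984). Power is P(X ≤ 10 | 108, .075) = .8135. The stated 80% is reproduced.

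**2. PEG: no true reduction from a blended standard.** Blended rate p = .15(1 − f) + q·f, where q is the standard tube rate without high-risk features. I take q = 6-8% from the IMRT-era range in section 1.5, as a proxy, and 10% as a more cautious assumption. The probability of a false claim is P(X ≤ 10 | 108, p):

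| q | f = 20% | f = 30% | f = 50% |
|---|---|---|---|
| 6% | p = .132: .141 | p = .123: .211 | p = .105: .411 |
| 8% | p = .136: .116 | p = .129: .162 | p = .115: .290 |
| 10% | p = .140: .095 | p = .135: .122 | p = .125: .194 |

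Every entry exceeds .056, as it must for any q below 15%.

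**3. PFS: the plan's own figure.** The plan states that "135 patients will provide 90% power to reject the null hypothesis that the experimental arm is inferior". With hazard λ = −ln(S)/2, λ0 = .2989 at 55% and λ1 = .2154 at 65%. With accrual A and further follow-up F, P(event) = 1 − [exp(−λF) − exp(−λ(A+F))]/(λA). For A = 3, F = 1, this is .510 and .406, so d0 = 68.9 and d1 = 54.8 events.

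Power = Φ[(λ0 − λ1 − 1.2816·λ0/√d0)/(λ1/√d1)] = Φ[(.0835 − .0461)/.0291] = .90.

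Section 9.2 also gives 2 years of accrual plus 1, which yields .86. I use 3 + 1, the schedule that reproduces the 90%.

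**4. PFS: high-risk-feature patients exactly at 55%.** The others are at 60-70%, the range that section 1.2 gives for more than 10 pack-years with N2-N3. It is assumed to apply here, although it includes N3 and is not specific to resected patients. Simulated pooled one-sided .10 test, N = 135, 3 + 1 years; the check runs give about .09 at 55% and .90 at 65%:

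| Others' 2-year PFS | f = 20% | f = 30% | f = 50% |
|---|---|---|---|
| 60% | .14 | .17 | .25 |
| 65% | .21 | .29 | .49 |
| 70% | .29 | .44 | .74 |

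With 2 + 1 years the 65% row is about .20, .27 and .45.

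**5. PFS: the other question.** Suppose instead that the regimen is exactly 10 points below a blended standard, .65(1 − f) + S·f. The pass probability for f = 20%, 30%, 50% is .066, .053, .03 if S = 60%; .10 throughout if S = 65%; and .146, .175, .242 if S = 70%. The error moves in either direction around .10.

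**6. Would a point-estimate condition help?** Suppose the high-risk-feature estimate must also fall on the right side of 15% or 55%. Keeping the two groups as separate binomials, PEG false claims at q = 6% go from .142 to .142 (f = 20%), .206 to .206 (30%) and .410 to .384 (50%). For PFS with the others at 65%, they go from .21 to .21, .29 to .27 and .49 to .37. This is little or no protection at 20-30%, and too little at 50%.

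**The case against.** The case for the plan has four parts.

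*The tests do not use Arm D.* A reader might infer that both co-primaries are tested against Arm D. They are not: Arm D appears only in the single-arm rationale, and both nulls come from elsewhere. This stands, and it adds a conflict to resolve between sections 9.1 and 9.2. It does not rescue the comparison, since both sources used chemoradiation.

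*RT alone is not stated to be these patients' standard.* A reader might infer that it is. Section 2.1 words the standard as 60-66 Gy with or without cisplatin, "typically recommended for Intermediate and High Risk patients (HPV-, >4 metastatic nodes, + extensive ENE, + margins"; section 1.5 calls the role of smoking after surgery unclear; the sentence on N2 concerns RTOG 0920; and ECOG 3311's allocation criteria are not given. This stands, so the point goes no further than a similarity statement that does not cover everyone.

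*A PFS bias towards the regimen is not shown.* A reader might infer one. The 60-70% in section 1.2 brackets the 65% benchmark, and step 5 gives errors on both sides of .10. In step 4 the pooled PFS is .56 to .625 (for example .8 × .55 + .2 × .60 = .56), so rejecting a pooled 55% is correct. What would be false is the cisplatin-specific wording. This stands.

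*The tube rates are weak.* The 6-8% is not stated to be RT alone, and section 1.2 reports 3% PEG dependence at 12 months after chemoradiation. The 15% may therefore be too high for everyone, which is a separate problem. The size in step 2 is illustrative; the direction rests on sections 1.3 and 1.4.

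**Conclusion.** The concern holds as a mismatch between the stated reference and the enrolled population. Arm D, as section 1.5 describes it, cannot represent both cohorts that the trial takes in, and one fixed chemoradiation benchmark is applied to a mixed group.

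For PEG, the direction favours the regimen wherever the standard tube rate without high-risk features is below 15%. The false-claim probability is about .10-.41 against .056, for an assumed 20-50% share and an assumed 6-10% rate. For PFS, the effect is conditional: about .14-.74 if high-risk-feature patients are at 55% and the others at 60-70%, but .03-.24 around a nominal .10 when judged against a blended standard. The pooled tests remain valid as tests against fixed 55% and 15%. They do not by themselves support a statement about replacing cisplatin.

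**What to change.** 1. **Reconcile the text.** Bring the single-arm rationale in section 9.1 into line with section 1.5 and section 9.2. State that Arm D is a reference only for patients with high-risk features, and name the actual source of each null. Do not assert RT alone as the standard for the remaining patients; sections 1.5 and 2.1 must first be reconciled.
2. **Report by risk feature.** Give 2-year PFS and 1-year PEG rate with confidence intervals for patients with high-risk features (more than 4 nodes, ENE above 1 mm or a positive margin), and separately for those admitted on N2 alone. State in advance where N3 patients, and N2c patients below 10 pack-years, are placed when they have none of these features. The smoking comparison in section 2.2 does not make this split.
3. **Word the conclusions to match.** Keep both pooled tests and report them as results against fixed 55% and 15%. Make a cisplatin-specific statement only with reference to the high-risk-feature estimate and its confidence interval. A point-estimate condition is not enough (step 6).

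**Cost.** Protocol and SAP wording, plus subset estimates from nodal, ENE and margin data already needed for registration. There are no new patients or procedures. The downside is precision. At 95 patients (about 70% of 135) a formal one-sided 10% PFS test would have about 80% power at 65%, and at 68 (about half) about 69%. For that reason this asks for an estimate and its interval, not a further test.
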